3.1.1 Administrative structure of the trial

Study sites will consist of specialized referral centres experienced in the management of ILD. A Coordinating Investigator, chosen among experts in the field of ILD, will be nominated and will be responsible for providing expert medical support for Investigators at different centres participating in this multicentre trial. Tasks and responsibilities of the Coordinating Investigator will be defined in a contract. Relevant documentation on all participating (Principal) Investigators and other important study personnel, including their curricula vitae, will be filed in Investigator Site File (ISF).

For Japan:

Tasks and functions assigned in order to organise, manage, and evaluate the trial will be defined according to BI SOPs. A list of responsible persons and relevant local information (as protocol reference, if applicable) can be found in the ISF.

HRCT eligibility criteria and HRCT pattern will be confirmed by central review prior to randomization (see [Section 3.3.4](#)). Central review of the HRCT images will be performed by two independent specialists in thoracic radiology with extensive expertise in the interpretation of HRCT. The reviewers will be blinded to demographic and clinical data of the patient. Cases of disagreement will be adjudicated by a third reviewer.

An independent blinded Adjudication Committee (AC) will review all fatal cases and adjudicate all deaths to either cardiac, respiratory or other causes (see [Section 5.3.7](#)). The AC will also review all adverse events categorized as major adverse cardiovascular events (MACE) (see Section 5.3.7).

A Data-Monitoring Committee (DMC), independent of the Sponsor will be in place until the database lock for the primary analysis after the last patient reaches the Week 52 visit (Part A: Visit 9) and will assess the progress of the clinical trial, including safety assessment at specified intervals, to recommend to the Sponsor whether to continue, modify, or stop the trial (see Section 5.3.7). The tasks and responsibilities of the DMC will be specified in a charter. The DMC will maintain written records of all its meetings.

Central laboratory facilities will handle all laboratory analyses of the trial. Samples for intermediate measurements (liver enzymes, creatinine) and pregnancy tests may be collected at the office of a local doctor using trial specific lab kits that will be sent to a central laboratory for analyses. These kits will be provided at each study visits as applicable to women of childbearing age.

An IRT (interactive response technology) vendor will be used in this trial.

The Sponsor has appointed a Trial Clinical Monitor, responsible for coordinating all required activities, in order to

- manage the trial in accordance with applicable regulations and internal SOPs,
- direct the clinical trial team in the preparation, conduct, and reporting of the trial,
- order the materials as needed for the trial,
- ensure appropriate training and information of local clinical monitors (CML), Clinical Research Associates (CRAs), and Investigators of participating countries.

Data Management and Statistical Evaluation will be done by Boehringer Ingelheim (BI) according to BI SOPs.

3.2 DISCUSSION OF TRIAL DESIGN, INCLUDING THE CHOICE OF CONTROL GROUP(S)

Placebo control

There is no approved treatment for ILD except for IPF. The management of ILD has been based on the suppression of inflammation with corticosteroids and immunomodulator/steroid-sparing agents or both. However, there are no controlled clinical trials to support the efficacy and safety of these therapies. In the current study, patients whose fibrosing ILD has worsened despite use of unapproved treatment for ILD will be eligible (see [Section 3.3.2](#)). To minimize potential impact on efficacy and safety assessments, treatment with unapproved anti-inflammatory/immunomodulatory treatment for ILD will be required to be discontinued and a wash-out period will be observed, if applicable, before randomization of the patient to either placebo or to nintedanib (see [Section 4.2.2](#)). As there is no targeted antifibrotic therapy currently indicated for the treatment of ILD in these patients, the use of placebo comparison in PF-ILD is considered justified. However, similar to the Phase III IPF studies, initiation of concomitant immunomodulatory treatment as medically indicated will be allowed for the management of worsening of the disease after the first six months of the trial (see Section 4.2.2).

Dose regimen

The dosing regimen to be investigated is the same as approved for IPF indication, i.e. 150 mg bid with the option of dose reduction to 100 mg and/or interruptions to manage adverse events (AEs). Exploration of higher dose(s) is not regarded feasible due to dose-limiting

toxicities (DLTs) observed in the oncology development program; testing of lower dose(s) is not considered based on lack of efficacy in IPF.

12 months treatment duration for primary assessment of benefit-risk of nintedanib in PF-ILD

The primary assessment of benefit-risk of nintedanib in patients with PF-ILD will be based on efficacy and safety data over 52 weeks (12 months) of study treatment. This is based on the assumptions that PF-ILD is similar to IPF and the treatment effect of nintedanib demonstrated in IPF will be reproduced in PF-ILD.

In IPF, the association between decline in FVC over one year and clinical outcome has been examined in the scientific literature ([R10-6539](#), [R06-4127](#), [P12-10347](#), [R14-1150](#), [P14-06844](#), [R14-1149](#)). While these publications do not, by stringent statistical criteria, prove that reduction in the annual rate of FVC decline is a surrogate for improved survival, they do strongly suggest that an increased rate and extent of decline in FVC at 12 months is associated with an increased risk of death. Due to the expected similarity in disease progression, especially for FVC decline and mortality, between PF-ILD patients and IPF patients, the proposed benefit-risk assessment over 12 months is regarded as the most appropriate period to detect a difference in the reduction of FVC decline between nintedanib and placebo in PF-ILD patients.

Additional data beyond 12 months will be collected while patients remain on blinded treatment to provide supportive longer term efficacy and safety data on the effect of nintedanib in a controlled manner, especially for the early enrollers to the study. Due to the varying length of follow-up in Part B of the trial, the efficacy measures incorporating data from Part A and Part B will focus on time to event endpoints.

The use of placebo control for this extended period is justified by the lack of approved ILD treatments and by the provision of the protocol that allows for the use of any of the unapproved medications utilized in the clinical practice to treat ILD, in case of worsening of the patient's ILD as assessed by the investigator (see [Section 4.2.2.1](#)).

Primary and main secondary endpoints

The primary endpoint of the study is the annual rate of decline in forced vital capacity (FVC). In clinical trials in IPF, FVC is an established efficacy parameter; mean changes in FVC over time are considered relevant to assess the effect of a pharmacologic intervention at population level ([P11-13635](#), [P12-10347](#), [R06-4126](#), [R06-4127](#)). FVC as primary endpoint has served as basis for worldwide regulatory approvals for nintedanib and pirfenidone in IPF ([P14-07514](#), [P10-13367](#)).

Similar to IPF, in other interstitial lung diseases (ILDs) the accelerated decline in lung function over time is considered consistent with disease progression and is thought to be associated with mortality ([R10-6539](#), [R06-4127](#), [P12-10347](#), [R14-1150](#), [P14-06844](#), [R14-1149](#)). In PF-ILD, and even more so for patients with PF-ILD with histologic usual interstitial pneumonia (UIP) pattern, it is expected that the placebo decline in FVC is similar to the

decline observed in patients with IPF and that nintedanib will slow the decline in FVC in a similar way as it does in IPF.

The main secondary endpoints are the absolute change from baseline in King's Brief Interstitial Lung Disease (K-BILD) total score at week 52, time to first acute ILD exacerbation or death over 52 weeks and time to death over 52 weeks. These endpoints are considered relevant to the assessment of the effect of nintedanib in PF-ILD and will provide the main supportive evidence to the primary endpoint assessment.

Enrichment design

Based on data suggesting that the HRCT pattern has a major impact on prognosis (see [Section 1.1](#)), the study population will be enriched for patients with HRCT with UIP-like fibrotic pattern only (see [Section 3.3.4](#)). An enrichment design will be used in order to increase the likelihood of detecting a clinically meaningful effect of nintedanib with the greatest statistical efficiency, therefore ensuring feasibility of the enrolment of patients with this rare disease. This enrichment design is consistent with the considerations for prognostic enrichment strategies in the Food and Drug Administration (FDA) Draft Guidance for Industry on Enrichment Strategies for Clinical Trials to Support Approval of Human Drug and Biological Products ([R13-0580](#)).

3.3 SELECTION OF TRIAL POPULATION

A total of approximately 600 patients with PF-ILD will be randomized (300 in the active dose group and 300 in placebo) in approximately 14 countries. Approximately 100 sites are each expected to include a minimum of 4-5 patients.

The study population will be enriched for patients with HRCT with UIP-like fibrotic pattern only: about 400 patients with PF-ILD with HRCT with UIP-like fibrotic pattern only and about 200 patients with PF-ILD with other HRCT fibrotic patterns will be randomized.

Patients with clinical diagnosis of IPF will be excluded from the current study (see [Section 1.1.3](#)).

A log of all patients enrolled into the trial (i.e. who have signed informed consent) will be maintained in the ISF at the investigational site irrespective of whether they have been treated with investigational drug or not.

3.3.1 Main diagnosis for trial entry

Outpatients aged ≥ 18 years with PF-ILD, defined as patients who present with features of diffuse fibrosing lung disease of $>10\%$ extent on HRCT and whose lung function and respiratory symptoms or chest imaging have worsened despite treatment with unapproved medications used in clinical practice to treat ILD, are eligible for inclusion if they fulfil all the inclusion criteria ([Section 3.3.2](#)) and do not present any of the exclusion criteria ([Section 3.3.3](#)).

Please refer to [Section 8.3.1](#) (Source Documents) for the documentation requirements pertaining to the in- and exclusion criteria.

3.3.2 Inclusion criteria

1. Written Informed Consent consistent with ICH-GCP and local laws signed prior to entry into the study (and prior to any study procedure including shipment of HRCT to reviewer).
2. Male or female patients aged ≥ 18 years at Visit 1.
3. Patients with physician diagnosed ILD who fulfil at least one of the following criteria for PF-ILD within 24 months of screening visit (Visit 1) despite treatment with unapproved medications used in clinical practice to treat ILD, as assessed by the investigator (refer to [Exclusion Criteria](#)):
 - a. Clinically significant decline in FVC % pred based on a relative decline of $\geq 10\%$
 - b. Marginal decline in FVC % pred based on a relative decline of $\geq 5\%-<10\%$ combined with worsening of respiratory symptoms
 - c. Marginal decline in FVC % pred based on a relative decline of $\geq 5\%-<10\%$ combined with increasing extent of fibrotic changes on chest imaging
 - d. Worsening of respiratory symptoms as well as increasing extent of fibrotic changes on chest imaging

[Note: Changes attributable to comorbidities e.g. infection, heart failure must be excluded. Unapproved medications used in the clinical practice to treat ILD include but are not limited to corticosteroid, azathioprine, mycophenolate mofetil (MMF), n-acetylcysteine (NAC), rituximab, cyclophosphamide, cyclosporine, tacrolimus].
4. Fibrosing lung disease on HRCT, defined as reticular abnormality with traction bronchiectasis with or without honeycombing, with disease extent of $>10\%$, performed within 12 months of Visit 1 as confirmed by central readers.
5. For patients with underlying CTD: stable CTD as defined by no initiation of new therapy or withdrawal of therapy for CTD within 6 weeks prior to Visit 1.
6. DLCO corrected for Haemoglobin (Hb) [visit 1] $\geq 30\%$ and $<80\%$ predicted of normal at Visit 2 (refer to [Appendix 10.1](#)).
7. FVC $\geq 45\%$ predicted at Visit 2 (refer to Appendix 10.1).

3.3.3 Exclusion criteria

1. AST, ALT $> 1.5 \times$ ULN at Visit 1
2. Bilirubin $> 1.5 \times$ ULN at Visit 1
3. Creatinine clearance <30 mL/min calculated by Cockcroft–Gault formula at Visit 1 (refer to [Appendix 10.2](#)).

[Note: Laboratory parameters from Visit 1 have to satisfy the laboratory threshold values as shown above. Visit 2 laboratory results will be available only after randomization. In case at Visit 2 the results do no longer satisfy the entry criteria, the Investigator has to decide whether it is justified that the patient remains on study drug. The justification for decision needs to be documented. Laboratory parameters that are

found to be abnormal at Visit 1 are allowed to be re-tested (once) if it is thought to be a measurement error (i.e. there was no abnormal result of this test in the recent history of the patient and there is no related clinical sign) or the result of a temporary and reversible medical condition, once that condition is resolved].

4. Patients with underlying chronic liver disease (Child Pugh A, B or C hepatic impairment).
5. Previous treatment with nintedanib or pirfenidone.
6. Other investigational therapy received within 1 month or 6 half-lives (whichever was greater) prior to screening visit (Visit 1).
7. Use of any of the following medications for the treatment of ILD: azathioprine (AZA), cyclosporine, MMF, tacrolimus, oral corticosteroids (OCS) >20mg/day and the combination of OCS+AZA+NAC within 4 weeks of Visit 2, cyclophosphamide within 8 weeks of Visit 2, rituximab within 6 months of Visit 2.
Note: Patients whose RA/CTD is managed by these medications should not be considered for participation in the current study unless change in RA/CTD medication is medically indicated (refer to [Inclusion Criterion #5](#))
8. Diagnosis of IPF based on ATS/ERS/JRS/ALAT 2011 Guidelines ([P11-07084](#)).
9. Significant Pulmonary Arterial Hypertension (PAH) defined by any of the following:
 - a. Previous clinical or echocardiographic evidence of significant right heart failure
 - b. History of right heart catheterization showing a cardiac index ≤ 2 l/min/m²
 - c. PAH requiring parenteral therapy with epoprostenol/treprostilin
10. Primary obstructive airway physiology (pre-bronchodilator FEV1/FVC < 0.7 at Visit 1).
11. In the opinion of the Investigator, other clinically significant pulmonary abnormalities.
12. Major extrapulmonary physiological restriction (e.g. chest wall abnormality, large pleural effusion)
13. Cardiovascular diseases, any of the following:
 - a. Severe hypertension, uncontrolled under treatment ($\geq 160/100$ mmHg), within 6 month of Visit 1
 - b. Myocardial infarction within 6 months of Visit 1
 - c. Unstable cardiac angina within 6 months of Visit 1
14. Bleeding risk, any of the following:
 - a. Known genetic predisposition to bleeding.
 - b. Patients who require
 - i. Fibrinolysis, full-dose therapeutic anticoagulation (e.g. vitamin K antagonists, direct thrombin inhibitors, heparin, hirudin)
 - ii. High dose antiplatelet therapy.
[Note: Prophylactic low dose heparin or heparin flush as needed for maintenance of an indwelling intravenous device (e.g. enoxaparin 4000 I.U. s.c. per day), as well as prophylactic use of antiplatelet therapy (e.g. acetyl salicylic acid up to 325 mg/day, or clopidogrel at 75 mg/day, or equivalent doses of other antiplatelet therapy) are not prohibited].
 - c. History of haemorrhagic central nervous system (CNS) event within 12 months of Visit 1.

- d. Any of the following within 3 months of Visit 1:
 - i. Haemoptysis or haematuria
 - ii. Active gastro-intestinal (GI) bleeding or GI – ulcers
 - iii. Major injury or surgery (Investigators judgment).
- e. Coagulation parameters: International normalized ratio (INR) >2, prolongation of prothrombin time (PT) and activated partial thromboplastin time (aPTT) by >1.5 x ULN at Visit 1.
15. History of thrombotic event (including stroke and transient ischemic attack) within 12 months of Visit 1.
16. Known hypersensitivity to the trial medication or its components (i.e. soya lecithin)
17. Patients with peanut allergy.
18. Other disease that may interfere with testing procedures or in the judgment of the Investigator may interfere with trial participation or may put the patient at risk when participating in this trial.
19. Life expectancy for disease other than ILD < 2.5 years (Investigator assessment).
20. Planned major surgical procedures.
21. Women who are pregnant, nursing, or who plan to become pregnant while in the trial.
22. Women of childbearing potential* not willing or able to use highly effective methods of birth control per ICH M3 (R2) that result in a low failure rate of less than 1% per year when used consistently and correctly as well as one barrier method for 28 days prior to and 3 months after nintedanib administration. A list of contraception methods meeting these criteria is provided in the patient information.
23. In the opinion of the Investigator, active alcohol or drug abuse.
24. Patients not able to understand or follow trial procedures including completion of self-administered questionnaires without help.

*A woman is considered of childbearing potential, i.e. fertile, following menarche and until becoming post-menopausal unless permanently sterile. Permanent sterilisation methods include hysterectomy, bilateral salpingectomy and bilateral oophorectomy.

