4.2.1.2 Management of liver enzyme elevation

Nintedanib can be associated with increased liver enzymes (see [Section 1.2](#)). Concomitant use of other drugs known to cause liver enzyme elevations should be evaluated. For a detailed guidance on how to manage liver enzyme elevations, please refer to [Table 4.2.1.2: 1](#).

Table 4.2.1.2: 1 Recommendations for managing liver enzyme elevations

	AST or ALT increase to			Signs of hepatic injury* (Section 5.3.6)
	>1.5x to <3x ULN	≥3x to <5x ULN and no signs of hepatic injury (see Section 5.3.6)	≥5x to <8x ULN and no signs of hepatic injury (see Section 5.3.6)	
Visit 2 (randomization)	Withdraw trial medication or justify continuation ¹	Withdraw trial medication	Withdraw trial medication	Withdraw trial medication
Any other Visit	Continue as planned ²	Reduce dose or interrupt trial medication ³	Interrupt trial medication	Withdraw trial medication
		Close observation ⁴ After 2 weeks or any time later	Close observation ⁴ After 2 weeks or any time later	CLINICAL EVALUATION OF HEPATIC-INJURY (Section 5.3.6)
	<3x ULN	≥3x ULN	< 3x ULN	≥3x ULN
	Reduced: return to initial dose. Interrupted: restart at reduced dose. Monitor bi- weekly for at least 8 weeks	Permanently discontinue trial medication Close observation ⁴	Restart at reduced dose Monitor weekly for 4 weeks, then bi-weekly for at least 8 weeks	Permanently discontinue trial medication. Close observation ⁴

Footnotes:

*Signs of hepatic injury are defined as

- ALT and/or AST ≥8 fold ULN
- ALT and/or AST ≥3 fold ULN and total bilirubin ≥2 fold ULN
- ALT and/or AST ≥3 fold ULN and unexplained INR >1.5
- ALT and/or AST ≥3 fold ULN and unexplained eosinophilia (>5%)
- ALT and/or AST ≥3 fold ULN and appearance of fatigue, nausea, vomiting, right upper abdominal quadrant pain or tenderness, fever and/or rash

¹ Investigator to confirm in writing that continuation is justified (e.g. intermittent fluctuation of transaminases).

² According to visit schedule. Consider additional control visits as adequate.

³ To be decided by Investigator, based on individual risk assessment.

⁴ Close observation: Re-test ALT and AST, alkaline phosphatase, total bilirubin, and eosinophils within 48 to 72 hours, then approximately 7 days, then approximately 2 weeks by using intermediate visit lab kit.

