Creatinine clearance will be calculated based on serum creatinine according to Cockcroft and Gault ([R96-0690](#), [Appendix 10.2](#)).

If laboratory values indicate abnormality, adequate and more frequent blood sampling may be performed at the discretion of the Investigator.

In case of liver function value elevations, close monitoring must be ensured by the Investigator. Refer to [Section 4.2.1.2](#) for monitoring elevations and [Section 3.3.4](#) for withdrawal criteria.

Laboratory analysis will be done using central laboratory services. Venous whole blood will be collected in appropriate syringes provided by the Sponsor through the assigned central laboratory. Details regarding centrifuge, processing, storage and shipment of samples will be determined by the central laboratory in accordance with the Sponsor. The Investigators will be informed and instructed by the central laboratory and detailed documentation will be included in the ISF.

5.3.4 *Electrocardiogram*

Resting 12 lead Electrocardiograms (ECGs) are conducted during the trial with site's own equipment. Rate, rhythm and repolarization changes have to be evaluated, compared to previous tracings, and assessed for clinical relevance.

Clinically relevant findings must be entered as adverse events.

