6. INVESTIGATIONAL PLAN

6.1 VISIT SCHEDULE

The trial consists of two parts: Part A and Part B. Part A will consist of Visits 2 through 9, which will occur within one year of randomization. Following completion of the week 52 visit (Visit 9), patients will continue to have study visits every 16 weeks (Part B) until the end of the trial. Intermediate lab tests for safety monitoring will be performed as needed until the end of the trial.

There is one screening visit (Visit 1; which may be preceded by a separate informed consent visit) and 8 visits (Visits 2 to 9) planned within the 52 weeks treatment period (Part A). Additional visits will occur every 16 weeks until the end of the trial. Furthermore, there are intermediate scheduled blood analyses and a follow-up Visit.

The trial will last until all patients completed the EOT_B visit and the Follow-up Visit as applicable. (see [Figure 3.1: 1](#)).

After giving his/her informed consent, the patient will be screened for inclusion (see [Section 3.3.2](#)) and exclusion criteria (see [Section 3.3.3](#)) for the trial at Visit 1 and Visit 2 (refer to [Flowchart Part A](#)).

Visit 2 can be performed once the results from central laboratory of Visit 1 and central HRCT review are obtained. If for any reason the screening phase for an individual patient lasts for more than 6 weeks, then the laboratory examination for Visit 1 has to be repeated before randomization. The screening phase must be no longer than 12 weeks. The patient will be randomized at Visit 2 if all inclusion and none of the exclusion criteria are fulfilled.

The results of laboratory parameters from Visit 2 will become available only after Visit 2. Therefore, laboratory results from Visit 2 cannot qualify as exclusion criteria; laboratory results from Visit 1 will be used instead. In case laboratory results of Visit 2 would retrospectively fulfil an exclusion criterion, the patient should not continue receiving trial medication unless continuation is justified in writing by the Investigator.

Visits 2, 3, 4 and 5 will occur every 2 weeks. Visit 6 will be scheduled 6 weeks later, Visits 7 and 8 are planned every 12 weeks and Visits 9 is planned after further 16 weeks. Visits 6a, 7a, and 8a are intermediate laboratory control visits.

After Visit 9, study visits will occur every 16 weeks (Part B) until the end of the trial. Visit numbers will continue with Visit 10, Visit 11, etc.

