- For patients who agreed to the optional HRCT-follow-up, HRCT should be done at V7 and V9.

Visit 3, 4, 5, 6, and 8 ('medium visits') procedures

Please note that not all medium visits are drug dispensation visits (please always refer to [Flowchart Part A](#)). However, compliance of patients regarding drug intake should always be reviewed (see also treatment compliance in [Section 4.3](#)).

- Physical examination including vital signs and HCRU interview will be performed.
- Adverse events and concomitant therapy since last visit will be reviewed and recorded.
- PROs will be scheduled prior to any other procedure and in the above described order and will be reviewed for completeness by site personal at Visits 6 and 8.
- Local dipstick pregnancy test (if applicable).
- Safety blood and urine samples will be collected and submitted to the central laboratory.
- At medium Visits 6 and 8, biomarker samples will be collected. The date and time of blood collection for biomarker samples will be recorded in the eCRF.
- At medium Visit 4, a PK sample will be collected. The patient needs to record exact date and clock time of medication intake the preceding three days on a PK-card provided at Visit 3. The date and time of blood collection and drug administration at the site will be recorded.
- At medium Visit 6, a PK-card will be provided to record exact date and clock time of medication intake three days preceding PK sampling at Visit 7.
- FlowScreen® spirometry (FVC) in the allowed time window will be performed.
- Non-elective hospitalization will be recorded.
- Acute ILD exacerbations will be recorded.
- 2 to 3 take home pregnancy tests (dipsticks) at Visit 8 will be dispensed.
- Treatment compliance will be reviewed by site personal at every visit (except at randomization visit and at 'a-Visits').
- Trial medication will be collected and/or dispensed according to Flowchart Part A.

Visit X and EOT_B procedures

- Physical examination including vital signs and HCRU interview will be performed.
- Adverse events and concomitant therapy since last visit will be reviewed and recorded.
- Local dipstick pregnancy test (if applicable).
- Safety blood and urine samples will be collected and submitted to the central laboratory.

Proprietary confidential information © 2018 Boehringer Ingelheim International GmbH or one or more of its affiliated companies

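### For a Visit 2 AST/ALT of ≥3x to <8x ULN without signs of hepatic injury, Protocol 3.3.3 and 6.1 allow justified continuation with no ceiling, while the Visit 2 row of Table 4.2.1.2: 1 calls for withdrawal (minor inconsistency)

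*Protocol*

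**What the plan says.** Three places in the protocol deal with abnormal liver enzymes in the Visit 2 sample.

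- **Protocol 3.3.3, note to exclusion criteria 1 to 3.** Eligibility rests on Visit 1 values (AST and ALT no higher than 1.5x ULN). If Visit 2 values no longer qualify, "the Investigator has to decide whether it is justified that the patient remains on study drug", and the reasons must be documented. The note covers AST/ALT, bilirubin and creatinine clearance together.
- **Protocol 6.1.** If Visit 2 results would have met an exclusion criterion, "the patient should not continue receiving trial medication unless continuation is justified in writing by the Investigator".
- **Protocol 4.2.1.2, Table 4.2.1.2: 1, Visit 2 row.** At >1.5x to <3x ULN the entry is "Withdraw trial medication or justify continuation", with a footnote requiring written confirmation by the investigator. At ≥3x to <5x, at ≥5x to <8x, and with signs of hepatic injury, the entry is withdrawal with no alternative and no footnote. The table's title is "Recommendations for managing liver enzyme elevations".

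Protocol 3.3.5.1 and 5.3.6.1 separately require the drug to be stopped when there are signs of hepatic injury. These are AST/ALT ≥8x ULN, or ≥3x ULN together with one of the listed bilirubin, INR, eosinophil or symptom findings.

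**The concern.** The liver-specific row is strict at Visit 2: from 3x ULN it leaves the investigator no discretion. The two general passages do leave discretion, and neither states where it ends. A site that has just received a Visit 2 result may well consult the eligibility note or the visit schedule first. If it follows either as written, it could justify continuation at, say, 4x ULN in writing and believe that it has complied.

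What is at stake is patient safety. The Visit 2 sample is drawn before dosing, but the result comes back after the first dose has been given in the clinic, so the decision concerns a patient already on drug. Protocol 2.3 states that severe drug-induced liver injury with a fatal outcome has been reported with nintedanib. The Visit 1 test may be up to 6 weeks old before a repeat is required (Protocol 6.1), so a rise between the two visits is possible.

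**Working it through.** No sample size, power or error-rate figure is involved. The check sets the texts side by side by level of the Visit 2 result.

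| Visit 2 AST/ALT | 3.3.3 note | 6.1 | Table 4.2.1.2: 1, Visit 2 row | 3.3.5.1 and 5.3.6.1 |
|---|---|---|---|---|
| >1.5x to <3x ULN | Investigator decides, documented | Stop unless justified in writing | Withdraw or justify | Not applicable |
| ≥3x to <5x ULN, no hepatic injury | Same, no ceiling | Same, no ceiling | Withdraw | Not applicable |
| ≥5x to <8x ULN, no hepatic injury | Same, no ceiling | Same, no ceiling | Withdraw | Not applicable |
| Signs of hepatic injury (including ≥8x ULN) | Same, no ceiling | Same, no ceiling | Withdraw | Mandatory stop |

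1. **Top row.** All texts agree.
2. **Bottom row.** The mandatory stop overrides the general wording, so nothing is open.
3. **The two middle rows.** The general wording allows an exception that the table does not, and the mandatory list does not reach this band.

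Next, does any other text settle the middle rows?

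- Protocol 3.3.3 and 6.1 do not cite the table.
- Protocol 4.2.1.2 introduces the table as guidance and states no precedence.
- SAP Table 6.2: 1, deviation A2.1, concerns Visit 1 values only.
- Deviation C4 flags failure to interrupt at ≥5x ULN, and C5 flags failure to discontinue permanently after signs of hepatic injury or when ≥3x ULN persists after 2 weeks or more of reduction or interruption. Neither contains a Visit 2 rule.

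Last, how long could continuation go unchecked? Protocol 6.1 states "Visits 2, 3, 4 and 5 will occur every 2 weeks". Visit 3 is planned for day 15 with a window of 3 days either side, that is day 12 to day 18. Counted from day 1, this is 12 − 1 = 11 to 18 − 1 = 17 days. At that visit "Safety blood and urine samples will be collected and submitted to the central laboratory" (Protocol 6.2.2), and the table's row for later visits then applies: "Reduce dose or interrupt trial medication" at ≥3x to <5x ULN, and interruption at ≥5x to <8x ULN.

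**The case against.** The strongest reply is that the texts fit together as a general rule and a specific limit. The 3.3.3 note asks whether continuation is justified; it does not say that it can be justified at any value. The table has a row made for Visit 2, and its footnote uses the same written-justification device as 6.1. Section 6.1 also makes stopping the default, and a site that withdraws the patient complies with all three texts.

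The SAP supports this reading. The second limb of C5 (≥3x ULN persisting after 2 weeks) matches the table and is absent from the mandatory list in 3.3.5.1, yet C5 treats it as a requirement of the protocol. C4 likewise matches the table. The sponsor therefore treats the table's content as binding despite its title.

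Backstops exist as well. For liver elevations Protocol 5.3.3 says "close monitoring must be ensured by the Investigator" and refers to 4.2.1.2 for how to monitor. The close-observation footnote there calls for re-tests within 48 to 72 hours, at about 7 days and at about 2 weeks, although its marks sit only in the later-visit part of the table. Under Protocol 4.2.1, dose reduction or interruption is available, so continuation need not be at full dose.

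Most of this stands. It establishes the table as the better reading and keeps the point small. It does not remove the difference in wording: the reader has to infer that the table governs, and the two sections that a site would consult on Visit 2 eligibility do not point to it.

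**Conclusion.** This is a minor internal inconsistency in a safety rule, confined to Visit 2 AST/ALT of ≥3x to <8x ULN without signs of hepatic injury. The table is best read as governing, but the protocol does not say so, and a site relying on 3.3.3 or 6.1 alone could keep on drug a patient whom the sponsor's own liver row would withdraw.

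Three stronger conclusions might be inferred, and the documents do not support them.

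- **That the protocol permits continuation at any enzyme level.** It does not: 3.3.5.1 and 5.3.6.1 require a stop once there are signs of hepatic injury, including any value ≥8x ULN.
- **That the number of affected patients can be stated or bounded.** No pre-dose rate of AST/ALT ≥3x ULN is given. The IPF figures in Protocol 1.2 (5.0% on nintedanib, 0.7% on placebo) come from 52-week treatment trials. Even the placebo rate is not shown to be a ceiling here, because methotrexate is allowed (4.2.2.1) and is named as raising transaminases (4.2.2.2). That few patients are affected is a judgement, resting on the 1.5x ULN limit at Visit 1 and on the narrow band.
- **That the primary analysis is affected.** Under SAP 7.4.1 all treated patients are analysed as randomised, with measurements after discontinuation included. A different stopping decision in a few patients does not change the analysis set or the method.

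**What to change.** Add the same sentence to the note in Protocol 3.3.3 and to the Visit 2 laboratory paragraph in Protocol 6.1:

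*For AST/ALT, continuation may be justified only at >1.5x to <3x ULN; at ≥3x ULN trial medication is withdrawn (see Table 4.2.1.2: 1).*

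This uses the sponsor's existing threshold and leaves the investigator's discretion for bilirubin and creatinine clearance as it is. The cost is one sentence in each of two sections. No visit, test or analysis changes.
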